5.4 Criteria for Initiation of Trial Treatment

The inclusion and exclusion criteria will be checked at the Screening visit. Eligible subjects will be enrolled before treatment start after verification of fulfilling all inclusion criteria without matching any exclusion criterion.

5.5 Criteria for Subject Withdrawal

5.5.1 Withdrawal From Trial Treatment

Subjects will be withdrawn from trial treatment for any of the following reasons:

- Confirmed PD per RECIST 1.1 or RANO for subjects with glioblastoma: Subjects should continue treatment beyond the initial determination of PD, through their next tumor assessment, provided:
 - a. There are no new Grade 2 or greater symptoms or significant worsening of existing symptoms.
 - b. There is no decrease in ECOG PS.
 - c. In the opinion of the Investigator, the subject does not require new anticancer therapy.

Subjects should be discontinued from treatment thereafter if further evidence of PD; however, continued treatment is possible in consultation with the Medical Monitor

- Occurrence of an exclusion criterion, which is clinically relevant and affects the subject's safety, if discontinuation is considered necessary by the Investigator and / or Sponsor
- Therapeutic failure requiring urgent additional cancer therapy
- Occurrence of Grade ≥ 3 ADRs or repetitive Grade 2 ADRs except as allowed as defined in Section 5.1.7.2
- Occurrence of AEs, at the Investigator's discretion
- Pregnancy
- Use of prohibited concomitant drug, as defined in Section 6.5.2, where the predefined consequence is withdrawal from the IMP
- Non-adherence / non-compliance to the trial protocol or trial requirements (see Section 6.9)
- Withdrawal of consent
- Participation in any other trial.

For subjects who miss ≥ 2 consecutive doses for medical reasons, the Medical Monitor should be consulted.

In the dose-escalation phase, the only subjects that may be replaced are those that do not complete the 21-day DLT observation period for reasons other than a DLT.

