5.1.1.2 Expansion Cohorts

The dose for the expansion cohorts was determined by the Sponsor based on the safety observations and PK / CCI data from the dose escalation part of the trial. The flat doses for extension part will be implemented after clearance of 20 mg/kg escalation cohort by the SMC. Except for the second-line NSCLC cohort, all subjects in expansion cohorts will be receiving 1200 mg (flat dose) every 2 weeks. Subjects in the second-line NSCLC cohort will be randomized to receive either 500 or 1200 mg every 2 weeks (see Section 3.4.1.1 for rationales).

Subjects in the expansion cohorts will receive MSB0011359C as a 1-hour IV infusion once every 2 weeks until PD has been confirmed by a subsequent scan, unacceptable toxicity, or occurrence of any criterion for withdrawal from the trial or the IMP (see Section 5.5).

Subjects who have experienced SD, PR, or CR should continue treatment through the end of 12 months, although additional treatment is possible. If the Investigator believes that a subject may benefit from treatment beyond 12 months, it may be permissible after discussion with the Medical Monitor and the Sponsor Medical Responsible. In the case of PD, subjects should continue treatment through their next tumor assessment, if they meet the criteria described in Section 5.5.1. If there is further evidence of PD thereafter, trial treatment should be discontinued; however, continued treatment is possible in consultation with the Medical Monitor. For subjects who achieve SD, a CR or PR on MSB0011359C therapy and then subsequently develop disease progression after stopping therapy, but prior to the end of the trial, 1 re-initiation course of treatment at the same dose and schedule and treatment duration up to 12 months is allowed at the discretion of the Investigator and agreement of the trial Medical Responsible (see Section 5.1.6). The Investigator will need to confirm that the benefit of re-initiating treatment outweighs any risk involved, such as that which led to initial treatment discontinuation. Moreover, for subjects in which BOR was SD, the Investigator should confirm no other reasonable treatment options are available.

For subjects in the melanoma, SCCHN, and TNBC cohorts only, symptom severity will be assessed using 2 patient-reported outcomes questionnaires:

- Patient Global Impression of Severity (PGIS)
- Select items from the EORTC QLQ-C30

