The foreseen treatment duration is until disease progression verified by a scan subsequent to the initial documentation of PD, unacceptable toxicity, or any criterion for withdrawal from the trial or IMP occurs (see Section 5.5). **Before stopping the treatment, progressive disease should be confirmed by imaging 4 to 6 weeks (preferably 6 weeks, but not later) after progression has been diagnosed according to RECIST 1.1.** If progression is based on the occurrence of a new lesion in an area not scanned at Baseline, a further on-study scan 6 weeks later should be considered before performing the 28-Day Safety Follow-up visit. Treatment may be continued despite progression according to RECIST 1.1 at any time if:

- There are no new symptoms or worsening of existing symptoms.
- There is no decrease in ECOG PS.
- The Investigator does not consider it necessary to administer a salvage therapy.

The treatment should be stopped immediately, if the subject does not tolerate MSB0011359C anymore or if therapeutic failure occurs, which requires urgent treatment with an additional drug or results in clinically significant progression / deterioration.

Tumor responses to treatment will be assigned based on the evaluation of the response of target, non-target, and new lesions according to RECIST 1.1 (all measurements should be recorded in metric notation) and secondarily using mRECIST for subjects in the HCC cohort (see Section 7.3.2). For subjects in the glioblastoma cohort, the assessment will be made according to RANO.

- To assess objective response, the tumor burden at baseline will be estimated and used for comparison with subsequent measurements. At baseline, tumor lesions will be categorized in target and non-target lesions according to RECIST 1.1 and secondarily using mRECIST for subjects in the HCC cohort. For subjects in the glioblastoma cohort, the assessment will be made according to RANO.

Results for these evaluations will be recorded with as much specificity as possible so that pre- and post-treatment results will provide the best opportunity for evaluating tumor response.

Any CR or PR should be confirmed according to RECIST 1.1 or RANO for subjects with glioblastoma. **In the case of a PR or CR, a confirmatory CT or MRI scan must be done no sooner than 4 weeks (preferably at the scheduled 6-week interval).**

The Investigator may perform scans in addition to a scheduled trial scan for medical reasons or if the Investigator suspects PD.

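### Protocol Sections 5.5.1 and 7.3 set different symptom and duration conditions for treatment beyond first progression, and no text says which applies

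*Protocol*

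**What the plan says.** Protocol Section 5.5.1 (Withdrawal From Trial Treatment) lists confirmed progression as a reason to withdraw, then adds: "Subjects should continue treatment beyond the initial determination of PD, through their next tumor assessment, provided" three conditions hold. They are:

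- symptoms: "There are no new Grade 2 or greater symptoms or significant worsening of existing symptoms"
- performance status: "There is no decrease in ECOG PS"
- other treatment: "In the opinion of the Investigator, the subject does not require new anticancer therapy"

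After that assessment, further evidence of progression should lead to discontinuation, although continuing is possible in consultation with the Medical Monitor.

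Protocol Section 7.3 (Efficacy Assessments) has a parallel list, introduced by "Treatment may be continued despite progression according to RECIST 1.1 at any time if". Its symptom condition is "There are no new symptoms or worsening of existing symptoms". Its performance status condition is worded as in 5.5.1. Its third condition is "The Investigator does not consider it necessary to administer a salvage therapy".

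Section 5.1.1.2 refers the reader to one of the two lists: "In the case of PD, subjects should continue treatment through their next tumor assessment, if they meet the criteria described in Section 5.5.1". Sections 5.1.6 and 7.1.2 say the same. The Synopsis refers only to criteria described in the protocol, which fits either list.

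**The concern.** Both lists govern whether a subject is dosed after a first RECIST 1.1 progression. Two of the three conditions agree in wording or substance; the symptom condition does not. Section 5.5.1 tolerates new Grade 1 symptoms and worsening that is not significant. Section 7.3 has no grade threshold and no qualifier on worsening. The force of the two texts also differs (*should* against *may*), and so does the period covered (the next assessment against any time).

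About 220 enrolling sites are planned (Protocol Section 2.1), and treatment decisions rest on local scan reads (Section 2.2.2). Sites consulting different sections could handle the same clinical picture differently. That would make post-progression dosing depend on site practice. It would also affect the quantities that run to the last dose: treatment duration, exposure and the window in which adverse events count as treatment-emergent. It is also an inconsistency in a patient-care instruction.

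**Working it through.** The plan states no figure on this point, so the check is a comparison of texts.

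**Step 1. Set the conditions side by side.**

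| Element | Section 5.5.1 | Section 7.3 |
|---|---|---|
| Force | should continue | may be continued |
| Period | through the next tumor assessment | at any time |
| Symptoms | no new Grade ≥ 2, no significant worsening | none new, none worse |
| ECOG PS | no decrease | no decrease |
| Other therapy | new anticancer therapy not required | salvage therapy not considered necessary |
| On further progression | discontinue, unless continued in consultation with the Medical Monitor | no such step in the list |

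**Step 2. Run the possible symptom states through both lists**, holding ECOG PS unchanged with no other therapy needed.

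| Symptoms at first progression | 5.5.1 list | 7.3 list |
|---|---|---|
| (a) nothing new or worse | met | met |
| (b) new Grade 1 symptom, or non-significant worsening | met | not met |
| (c) new Grade ≥ 2 symptom, or significant worsening | not met | not met |

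The symptom conditions part only in state (b). If ECOG PS has fallen or other therapy is needed, both lists fail and the symptom wording makes no difference.

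**Step 3. Check whether scope separates them.** Section 5.5.1 speaks of the initial progression. Section 7.3 says at any time, which includes the initial progression, so the lists overlap there.

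**Step 4. Check for a precedence rule.** Sections 5.1.1.2, 5.1.6 and 7.1.2 cite 5.5.1 for the continuation criteria. Section 7.3 refers to Section 5.5 for withdrawal criteria and later to Section 5.1, yet still prints its own list. No sentence says which list governs.

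**Step 5. Bound the exposure at stake per affected subject.** Dosing is every 2 weeks. Scans are every 6 weeks to 12 months and every 12 weeks after that (Protocol Table 2, Sections 7.1.2.1 and 7.1.2.2). From first progression to the next scheduled scan:

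- first 12 months: 6 / 2 = 3 dosing intervals
- after 12 months: 12 / 2 = 6 dosing intervals

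If the confirmatory scan is taken in the 4-to-6-week window of Section 7.3, the span is 4 / 2 = 2 to 6 / 2 = 3 intervals. These are upper bounds on the difference between two sites, because the second site need not stop at once.

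**Step 6. Trace this to the analyses.** The on-treatment period ends 30 days after the last dose, or the day before subsequent anticancer drug therapy if that is earlier (Protocol Section 8.5.4.1). SAP Section 9.8 uses the same 30 days, and 90 days for immune-related events. SAP Section 13 measures duration as (last dose − first dose + 14) / 7 weeks. If the last dose moves by 6 weeks, duration moves by 6 weeks. The window end moves by 6 × 7 = 42 days, unless new therapy closes it sooner. By contrast, best overall response is taken until first documented progression (SAP Section 14.1), and PFS ends at the first progression date (SAP Section 14.3).

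**The case against.** A reader might infer that the same subject is continued under one section and stopped under the other. The documents do not support that. Section 7.3 grants a permission; it does not say that a subject who fails the list must stop. It has its own immediate-stop rule, for intolerance or for therapeutic failure that needs urgent additional treatment or brings clinically significant deterioration. A new Grade 1 symptom alone does not meet that rule. It also asks for imaging confirmation before treatment is stopped, with no symptom condition, and later leaves room for the Investigator's decision. The conflict is therefore between an instruction to continue and failure of a listed condition for being allowed to continue.

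A reader might also infer that confirmation of progression or the immune-related reads depend on which list a site follows. The request for confirmatory imaging does not vary with symptoms. Section 7.3.1 leaves irRECIST to independent radiology review, and no visible text makes it a primary endpoint.

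Finally, the cross-references lean towards 5.5.1, which is the section titled for treatment withdrawal. That is fair and reduces the risk of divergence. It does not remove it, because 7.3 restates the conditions differently in operative text and no precedence is given.

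These points limit the consequences. The difference in conditions stands, as does the difference in duration.

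**Conclusion.** The inconsistency is real and minor. In state (b), a subject should continue under 5.5.1 but fails a listed condition for continuing under 7.3. Separately, the open-ended period in 7.3 does not match the discontinuation step in 5.5.1 after further progression.

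The effect is on post-progression exposure, treatment duration and the on-treatment adverse event window: at most about 3 dosing intervals per affected subject to the next scheduled scan in the first year, and about 6 later. It would be wrong to count every subject with a new Grade 1 symptom at progression. Only those with unchanged ECOG PS and no need for other therapy are affected, and Medical Monitor and Investigator discretion narrows the group further. The documents give no frequency, so no total can be stated.

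Best overall response and PFS are not materially affected. That rests on the SAP definitions, which are investigator-assessed and written for the cervical cancer outputs. For the protocol's IRC-adjudicated primary endpoint, it assumes that the committee does not date first progression later than the local read.

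**What to change.** Reconcile Protocol Sections 5.5.1 and 7.3 to one set of conditions covering symptoms, force, period and what happens on further progression. State it once, and have the other section cross-refer to it without restating it. Point the Synopsis reference to the same place. The symptom threshold and the duration rule are for the sponsor's clinical team; no view is taken here on which is right. The cost is protocol wording only: no sample size, endpoint or analysis definition changes.

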5.5.2 Withdrawal From the Trial

Subjects may withdraw from the trial at any time without giving a reason. Withdrawal of consent will be considered withdrawal from the trial.

A subject must be withdrawn if any of the following occur during the trial:

- Withdrawal of the subject's consent
- Participation in any other therapeutic trial during the treatment duration of this trial; however, subjects will continue to be followed for survival

If a subject fails to attend scheduled trial assessments, the Investigator must determine the reasons and the circumstances as completely and accurately as possible.

In case of withdrawal from the trial, the assessments scheduled for the last visit (28-Day Safety Follow-up visit) should be performed (see Section 7.1.3), if possible, with focus on the most relevant assessments. In any case, the appropriate 28-Day Safety Follow-up electronic case report form (eCRF) visit must be completed. In case of withdrawal, subjects will be asked to continue safety and survival follow-up, which includes the collection of data on survival and subsequent anticancer therapy. After completion of the Follow-up period or after the End-of-Treatment visit, whatever is applicable, the appropriate eCRF section for Trial Termination must be completed.

If a subject is withdrawn prior to disease progression for any reason in the expansion part of the trial, the subject will not be replaced. In the dose-escalation part, the only subjects that may be replaced are those that do not complete the 21-day DLT observation period for reasons other than a DLT.

After primary analyses are completed, subjects may enroll into a roll-over trial before planned end of the trial or withdrawn after they have at least completed the Safety Follow-up at 10 Weeks (± 2 weeks) after Last Treatment.

5.6 Premature Termination of the Trial

The whole trial may be discontinued prematurely in the event of any of the following:

- New information leading to unfavorable risk-benefit judgment of the IMP, for example, due to
 - evidence of inefficacy of the IMP,
 - occurrence of significant previously unknown adverse reactions or unexpectedly high intensity or incidence of known adverse reactions, or
 - other unfavorable safety findings.

(Note: Evidence of inefficacy may arise from this trial or from other trials; unfavorable safety findings may arise from clinical or non-clinical examinations, for example, toxicology.)

- Sponsor's decision that continuation of the trial is unjustifiable for medical or ethical reasons
- Poor enrollment of subjects making completion of the trial within an acceptable time frame unlikely
- Discontinuation of development of the Sponsor's IMP

Health Authorities and Independent Ethics Committees (IECs) / Institutional Review Boards (IRBs) will be informed about the discontinuation of the trial in accordance with applicable regulations.

The whole trial may be terminated or suspended upon request of Health Authorities.

5.7 Definition of End of Trial

If the trial is not terminated for a reason given in Section 5.6, the end of the trial is defined as when subjects are either enrolled into a roll-over trial or withdrawn after completing at least the Safety Follow-up visit at 10 Weeks (\pm 2 weeks) after Last Treatment.

6 Investigational Medicinal Product and Other Drugs Used in the Trial

The term “Investigational Medicinal Product” refers to an active substance or a placebo being tested or used as a reference therapy in a clinical trial, including products that have a marketing authorization but are formulated, packaged, or administered differently from the authorized form, used for an unauthorized indication, or used to gain further information about the authorized form. The only IMP used in this trial is MSB0011359C.

6.1 Description of the Investigational Medicinal Product

MSB0011359C drug product is provided as either a sterile freeze-dried or a sterile liquid formulation.

Each vial of Powder for Concentrate for Solution for Infusion (freeze-dried formulation) is packaged in United States Pharmacopeia (USP) and European Pharmacopeia (Ph Eur) type I glass vials. Each vial is filled with 45 mg of MSB0011359C (45 mg/vial) as preservative-free powder containing histidine, trehalose dihydrate, sodium chloride, L-methionine and polysorbate 20 (Tween 20). The vials are closed with a rubber stopper in lyophilization format complying with USP and Ph Eur and sealed with an aluminum plastic crimping cap. Only excipients that conform to the current USP and / or Ph Eur are used for MSB0011359C drug product.

The Concentrate for Solution for Infusion (liquid formulation) is packaged at a 10 mg/mL concentration in USP / Ph Eur type I 50R vials that are filled with drug product solution to allow an extractable volume of 60 mL (600 mg/60 mL). The vials are closed with rubber stoppers with the same composition as used for freeze-dried formulation, but in serum format complying with USP and Ph Eur with an aluminum crimp seal closure.

The liquid formulation, compared with the freeze-dried formulation, has the same composition in terms of excipients, qualitatively and quantitatively, except for the addition of water. Of note, there is no change to the drug substance process.

For applications in clinical studies, the freeze-dried formulation must be reconstituted with 4.5 mL water for injection and further diluted with 0.9% saline solution (sodium chloride injection) supplied in an infusion bag. The liquid formulation is diluted directly with 0.9% saline solution.

The estimated volumes of delivery are anticipated to be no more than 250 mL, which are clinically acceptable. For subjects requiring doses that would exceed the maximum allowable concentration in 250 mL (eg, subjects in the 30 mg/kg cohort), MSB0011359C may be diluted in 0.9% sodium chloride to a total volume of 500 mL provided the final concentration range is 0.16 mg/mL to 9.6 mg/mL. Detailed information on infusion preparation and administration are provided in the protocol and manual of preparation.

Subjects who received the freeze-dried formulation before the introduction of the liquid formulation will remain on the freeze-dried formulation.

6.2 Dosage and Administration

Subjects will receive IV infusion of MSB0011359C over 1 hour (-10 minutes / +20 minutes, that is, over 50 to 80 minutes) once every 2 weeks as detailed in the Schedules of Assessments (see Table 1 and Table 2). Subjects enrolled in the 30 mg/kg and the 2400 mg flat-dose cohorts who require a drug volume of 500 mL may have a total infusion time of up to 120 minutes in the absence of any history of infusion reaction. Modifications of the infusion rate due to infusion-related reactions are described in Section 6.5.4. In order to mitigate potential infusion-related reactions, premedication with an antihistamine and with paracetamol (acetaminophen) (for example, 25-50 mg diphenhydramine and 500-650 mg paracetamol [acetaminophen] IV or oral equivalent) approximately 30 to 60 minutes prior to each dose of MSB0011359C is mandatory for the first 2 infusions and is optional and at the discretion of the Investigator after the second infusion (premedication is optional for all infusions for subjects in the NSCLC biomarker cohort being treated at the US NCI). If Grade ≥ 2 infusion reactions are seen during the first two infusions premedication should not be stopped. Steroids as premedication are not permitted. Special precautions for monitoring of subjects and management of infusion-related reactions / hypersensitivity including modifications of the infusion rate and stopping of trial drug are described in Section 6.5.4 and subsections.

The starting dose of MSB0011359C in the dose-escalation portion is 1 mg/kg (dose-escalation according to 3 + 3 design up to 30 mg/kg is intended) and the treatment cycle will be 2 weeks (14 days). The first subject of each cohort will be observed for at least 5 days before the second subject can be treated. Subsequent subjects may receive first dosing at no less than 48-hour intervals between subjects. The dose of MSB0011359C in the expansion will be determined from the dose-escalation portion of the trial.

For the dose-escalation cohorts (except for the 2400 mg flat-dose cohort), the dose of MSB0011359C will be calculated based on the weight of the subject determined on the day prior to or the day of each drug administration. Subjects will receive MSB0011359C once every 2 weeks until confirmed progression, unacceptable toxicity, or any criterion for withdrawal from the trial or IMP occurs (see Section 5.5). Subjects who have experienced SD, PR, or CR should continue treatment through the end of 12 months, although additional treatment is possible. If the Investigator believes that a subject may benefit from treatment beyond 12 months, it may be permissible after discussion with the Medical Monitor and the Sponsor Medical Responsible.

Following safety and PK analysis of the Escalation cohorts, a flat dose of 1200 mg/infusion was chosen for all expansion cohorts, except for the NSCLC second-line cohort, in which 40 subjects will receive 500 mg/infusion and 40 subjects will receive 1200 mg/infusion.

For subjects who achieve SD, a PR or CR on MSB0011359C therapy and then subsequently develop disease progression after stopping therapy, but prior to the end of the trial, 1 re-initiation course of treatment at the same dose and schedule and treatment duration up to 12 months is allowed at the discretion of the Investigator and agreement of the trial Medical Responsible (see Section 5.1.6). The Investigator will need to confirm that the benefit of re-initiating treatment outweighs any risk involved, such as that which led to initial treatment discontinuation. Moreover, for subjects in which BOR was SD, the Investigator should confirm no other reasonable treatment options are available. Subjects re-initiating treatment should be assessed according to the Schedules of Assessment for the Expansion portion of the trial starting at Week 1, Day 1 (see Table 2).

